8.7 Missing Data Analysis

No missing data is expected for the primary outcome. Data on whether participants received the first XR-NTX injection while on the treatment unit is always available.

9.0 IMPLEMENTATION OUTCOME ANALYSIS

Implementation outcomes, such as participant ratings of acceptability and satisfaction with treatment, and clinicians' ratings of knowledge and attitudes toward XR-NTX and XR-NTX induction methods before and after sites' protocol participation, will be modelled as continuous outcomes using mixed-effects linear regression models, with random intercepts for site. Additional

implementation outcome measures including acceptability and barriers are measured qualitatively.

10.0 SAFETY OUTCOMES AND ANALYSIS

Safety outcomes for this study include targeted safety events, serious adverse events, death, injection site abnormalities, overdoses, suicide risk, and pregnancy. Safety outcomes analysis will be performed on the safety analysis population as defined in Section 3.1.4. Safety outcomes will be summarized by induction procedure (SP or RP) and overall. The induction procedure will be determined by the induction procedure the site was assigned to at the time of participant enrollment.

10.1 Targeted Safety Events

Study defined targeted safety events (TSEs) are defined in Section 3.2.7. TSEs will be summarized by presenting the number and types of TSEs, relatedness to study medication, SAE classification, and number of participants experiencing TSEs by induction procedure and phase (i.e., Screening, Baseline, Induction and Post-Induction). Comparison of TSEs by induction procedure will be conducted using Fisher's exact test.

Detailed listings of TSEs by induction procedure will be provided. The listing will include Participant ID, date of IC, date of enrollment, date of TSE, TSE type and detail, severity of TSE, relatedness to study medication, SAE classification, and any additional comments collected on the form.

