3.1.4 Safety Population

This study records safety events for all participants that sign IC. Therefore, the safety population consists of all participants who sign IC.

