3.2 General Definitions

3.2.1 Induction Phase

The induction phase Day 1 is defined as the day of the admission (E97ADMDT) as recorded on the ENRC or ENRD forms. The induction phase for enrolled participants begins with day of admission (induction phase Day 1) and ends on the day of XR-NTX receipt or day of failure of the induction protocol. The maximum length of the induction phase is 30 days (Day 1 – Day 30). Note that the end of the induction phase does not always coincide with the participants being discharged from the unit.

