Targeted safety events, overdoses and SAEs, related to study medications	Frequency of targeted safety events, overdose episodes and SAEs by relationship to study medication during the induction period and during eight weeks of post-induction treatment	RP and SP will produce equivalent rates of targeted safety events and SAEs during the induction and during the first eight weeks of treatment with XR-NTX. Significance/Rationale: Careful documentation of SAEs, targeted safety events, and overdose episodes, would be considered essential safety data, and important component of a comparative effectiveness trial.
Receive second and third injections (binary: did or did not receive second and third dose of XR-NTX)	Proportion of participants that receive second and third injection of XR-NTX (at 4 weeks and 8 weeks, from first injection)	Participants in RP and SP will have comparable rates of treatment retention. Significance/Rationale: Because there is no difference in tolerability of the first and second XR-NTX injections in both study arms, we do not expect differential treatment dropout.
Use of opioids over time during the 8-week of post-induction treatment while on study medication (Weekly TLFB, confirmed by urine drug screens when available)	Percent of participants positive for opioids using weekly TLFB during eight weeks of post-induction, and urine drug screens at week 4 and 8.	RP and SP will produce comparable levels of opioid use. Significance/Rationale: XR-NTX produces complete blockade of opioid effects, so that during treatment with monthly injections, opioid use can be expected to be minimal and no different between study arms.

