	Number of TSEs				
	Type of TSE ⁷				
	Fall event ³				
	Acute change in mental status ⁴				
	Acute medical complication likely exacerbated by the stress of withdrawal ⁵				
	Acute psychiatric symptoms ⁶				
	Relationship of TSE to study medication ⁷				
	No				
	Yes				
	TSE defined as serious adverse event ⁷				
	No				
	Yes				

Table 52: Summary of Targeted Safety Events by Study Phase and Induction Procedure

Study Phase		Induction Procedure		Total (N=XX)	p-Value ⁸
		Standard (N=XX)	Rapid (N=XX)		
Screening Phase	Number of participants with at least one targeted safety event (TSE) ¹	N (X.x%)			
	Number of participants with at least one TSE of the following types ²				
	Fall event ³	N (X.x%)			
	Acute change in mental status ⁴				
	Acute medical complication likely exacerbated by the stress of withdrawal ⁵				
	Acute psychiatric symptoms ⁶				
	Number of participants with at least one TSE related to study medication ¹	N (X.x%)			
	Number of participants with at least one TSE defined as serious adverse event ¹	N (X.x%)			
	Number of TSEs	N			
	Type of TSE ⁷				
	Fall event ³	N (X.x%)			
	Acute change in mental status ⁴				
	Acute medical complication likely exacerbated by the stress of withdrawal ⁵				
	Acute psychiatric symptoms ⁶				
	Relationship of TSE to study medication ⁷				
	No	N (X.x%)			
	Yes				
	TSE defined as serious adverse event ⁷				
	No	N (X.x%)			
	Yes				

Table 52: Summary of Targeted Safety Events by Study Phase and Induction Procedure

Study Phase	Induction Procedure			
	Standard (N=XX)	Rapid (N=XX)	Total (N=XX)	p-Value⁸
Induction Phase	Number of participants with at least one targeted safety event (TSE) ¹	N (X.x%)		
	Number of participants with at least one TSE of the following types ²			
	Fall event ³	N (X.x%)		
	Acute change in mental status ⁴			
	Acute medical complication likely exacerbated by the stress of withdrawal ⁵			
	Acute psychiatric symptoms ⁶			
	Number of participants with at least one TSE related to study medication ¹	N (X.x%)		
	Number of participants with at least one TSE defined as serious adverse event ¹	N (X.x%)		
	Number of TSEs	N		
	Type of TSE ⁷			
	Fall event ³	N (X.x%)		
	Acute change in mental status ⁴			
	Acute medical complication likely exacerbated by the stress of withdrawal ⁵			
	Acute psychiatric symptoms ⁶			
	Relationship of TSE to study medication ⁷			
	No	N (X.x%)		
	Yes			
	TSE defined as serious adverse event ⁷			
	No	N (X.x%)		
	Yes			

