Table 52: Summary of Targeted Safety Events by Study Phase and Induction Procedure

Study Phase	Induction Procedure			
	Standard (N=XX)	Rapid (N=XX)	Total (N=XX)	p-Value⁸
Post-Induction Phase	Number of participants with at least one targeted safety event (TSE) ¹	N (X.x%)		
	Number of participants with at least one TSE of the following types ²			
	Fall event ³	N (X.x%)		
	Acute change in mental status ⁴			
	Acute medical complication likely exacerbated by the stress of withdrawal ⁵			
	Acute psychiatric symptoms ⁶			
	Number of participants with at least one TSE related to study medication ¹	N (X.x%)		
	Number of participants with at least one TSE defined as serious adverse event ¹	N (X.x%)		
	Number of TSEs	N		
	Type of TSE ⁷			
	Fall event ³	N (X.x%)		
	Acute change in mental status ⁴			
	Acute medical complication likely exacerbated by the stress of withdrawal ⁵			
	Acute psychiatric symptoms ⁶			
	Relationship of TSE to study medication ⁷			
	No	N (X.x%)		
	Yes			
	TSE defined as serious adverse event ⁷			
	No	N (X.x%)		
	Yes			

¹ The percentage was calculated based on the denominator of the number of enrolled participants.

² The percentage was calculated with the denominator as the number of participants with TSEs.

³ Likely related to medical/psychiatric condition such as dizziness, confusion with head injury.

⁴ Disorientation, amnesia, cerebrovascular accident, coma.

⁵ Hypertensive crisis, hypotensive event with medical sequelae such as fall and/or requiring urgent fluid resuscitation, severe chest pain, cardiac arrhythmia, acute respiratory decompensation, asthma attack, diabetic ketoacidosis, severe hypoglycemia.

⁶Acute psychiatric symptoms (i.e., psychosis, hypomania, severe agitation, violence).

⁷The percentage was calculated with the denominator as the number of TSEs.

⁸p-value is from Fisher's Exact Test.

Table 53: Summary of Study Injection Site Examinations

	Induction Procedure		
	Standard (N=XX)	Rapid (N=XX)	Total (N=XX)
Number of participants with at least one abnormal injection site ¹	N (X.x%)		
Number of abnormal injection sites	N		
Symptom experienced ²			
None	N (X.x%)		
Pain			
Tenderness			
Erythema/Redness			
Swelling			
Induration			
Abscess			
Necrosis			
Bruising			
Pruritus			
Nodule			
Hematoma			
Sterile abscess			
Cellulitis			
Warmth			
Other			
Severity ²			
Grade 1 - Mild	N (X.x%)		
Grade 2 - Moderate			
Grade 3 - Severe			

¹ Percentages were calculated based on number of enrolled participants.

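### The Induction row of the targeted safety event table compares about 6 planned days in RP with about 13 in SP, and an equivalence hypothesis is met only by a Fisher p-value with no interval

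*SAP*

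**What the plan says.** SAP 10.1 summarises the "number of participants experiencing TSEs by induction procedure and phase (i.e., Screening, Baseline, Induction and Post-Induction", and adds: "Comparison of TSEs by induction procedure will be conducted using Fisher's exact test". The shell in SAP 19.1.9, "Table 52: Summary of Targeted Safety Events by Study Phase and Induction Procedure", has Overall, Screening, Induction and Post-Induction blocks under one p-value column, which a footnote attributes to Fisher's test. It has no column for an interval, a rate or time at risk.

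SAP 3.2.1 starts the induction phase on the day of admission and says that it "ends on the day of XR-NTX receipt or day of failure of the induction protocol", with a maximum of 30 days. SAP 12 places the planned end at about Day 6 in RP and Day 13 in SP. Under SAP 3.2.2, post-induction begins the next day and lasts 56 days in both arms.

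The hypothesis in SAP Table 5 (Protocol Table 3 is the same) is that "RP and SP will produce equivalent rates of targeted safety events and SAEs during the induction" and the eight weeks that follow. No margin is stated.

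On populations, SAP 3.1.4 says that "the safety population consists of all participants who sign IC". SAP 10.0 assigns the arm from the site's procedure at enrollment, and Table 52 notes: "The percentage was calculated based on the denominator of the number of enrolled participants".

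**The concern.** On planned timing, Days 7 to 13 after admission count as induction in SP and as post-induction in RP. A participant-level proportion within the Induction block therefore sets a short window against one about twice as long. If daily risk were the same, RP would show fewer affected participants in that row simply because its phase is shorter, and the p-value could make this look like a safety advantage. This matters because Protocol Appendix B allows that withdrawal may be more severe in RP, and precipitated withdrawal is one of the targeted events.

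Separately, a hypothesis of equivalent rates is paired only with a test of difference. With few events, such a test is often non-significant whether or not risk differs, and without an interval the reader cannot see what the data exclude.

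A smaller point concerns populations. Events may come from people who consented but never enrolled. They have no defined arm and are not in the denominator.

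**Working it through.** **Arm sizes.** The design matrix has 5+4+3+2+1+0 = 15 RP cells out of 30. At 15 participants per cell this gives 225 RP and 225 SP, as Protocol 8.0 states. The documents give no event rate, power or margin for targeted safety events, so every rate below is an assumption.

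**Exposure in the Induction block.** The planned ratio is 6/13 = 0.46. Failures end induction early. Using the SAP 12 success rates (0.55 SP, 0.70 RP) and assumed failure days of 4 to 10 in SP and 3 to 6 in RP, mean days are:
- SP: 0.55×13 + 0.45×4 = 8.95, up to 0.55×13 + 0.45×10 = 11.65
- RP: 0.70×6 + 0.30×3 = 5.1, up to 0.70×6 + 0.30×6 = 6.0

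The ratio then runs from 5.1/11.65 = 0.44 to 6.0/8.95 = 0.67. Event capture starts at consent. If consent falls on Day 4, the planned ratio is 3/10 = 0.30.

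**Exposure in the Overall block.** Planned induction plus post-induction is 6+56 = 62 days v 13+56 = 69 days, a ratio of 0.90.

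**False advantage to RP at equal daily risk.** The proportion affected is 1 − (1 − h)^days. The table gives the exact probability that a two-sided 5% Fisher test is significant in RP's favour, with 225 per arm.

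| Assumed daily hazard h | 6 v 13 days: RP v SP affected | Significant for RP | 6 v 9 days: RP v SP affected | Significant for RP |
|---|---|---|---|---|
| 0.2% | 1.2% v 2.6% | 10% | 1.2% v 1.8% | 3% |
| 0.5% | 3.0% v 6.3% | 32% | 3.0% v 4.4% | 8% |
| 1% | 5.9% v 12.2% | 61% | 5.9% v 8.6% | 16% |

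For comparison, when the participant proportions are truly equal (3% to 15%), the exact test is significant in a given direction in 1.2% to 1.8% of trials.

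**A true excess in RP.** At 6 v 13 days, with SP proportions of 3% to 15%, a doubled RP daily rate gives a significant RP excess in about 1% of trials and a significant result favouring RP in 2% to 4%.

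**What non-significance excludes.** For a participant-level doubling from 3% to 6%, Fisher power is 26%. With 11/225 events in each arm, p = 1.00, but the 95% CI for the difference is −4.0 to +4.0 percentage points and for the risk ratio 0.44 to 2.26. Against 11 SP events, RP would need 23 for p < 0.05.

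With 190 SP and 225 RP (the counts in the Table 55 shell), the Fisher probabilities for SP proportions of 3% to 15% move by no more than about 3 points.

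**The case against.** Four objections carry weight.

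- A nearly balanced comparison is already planned. The Overall block spans about 62 v 69 days and keeps every event, and the listing gives phase and date. A reader might infer that the whole safety comparison is biased or that RP reactions are hidden. Neither holds: the exposure problem lies in the phase rows, and the rule that events after the injection day count as post-induction applies to both arms.
- Risk per participant over a whole procedure is a legitimate estimand, because a shorter induction is part of what RP offers. That stands. The stated hypothesis, however, concerns rates, and the row labels do not tell the reader that the windows differ.
- The magnitudes rest on assumed hazards, constant over time. RP titrates naltrexone on Days 3 to 6, while SP Days 6 to 13 are washout, so hazards may well differ by day. The figures show what the row can do, not what it will do. They also ignore clustering by site.
- A reader might infer that the SAP intends to declare equivalence from a non-significant p-value. No sentence says so. SAP 11 calls the key secondary outcomes non-confirmatory, and Protocol 2.5 says the trial is not powered for new safety signals. The caution in SAP 11 is about multiple testing, though, and does not replace an interval.

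A fixed window is not free of bias either. Targeted safety events are not among the items that SAP 2.2.2 lists for retrospective abstraction, and consent may come as late as Day 4. Daily observation ends sooner in RP, and participants who fail induction return only at Weeks 4 and 8.

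**Conclusion.** The point holds for the Induction and Post-Induction rows of Table 52, which compare different stretches of time by arm. At equal daily risk the Induction p-value leans towards RP. How far depends on unknown quantities: from about 3%, close to nominal, at a 0.2% daily hazard and 6 v 9 days, to about 61% at 1% and 6 v 13 days. These results assume constant hazards, 225 per arm, every participant having the stated number of days, and no site effect. The Overall row is largely sound on exposure.

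A hypothesis of equivalence with only a difference test, no margin and no interval cannot be supported by a non-significant result at these event counts. That is a gap in presentation and wording, not evidence of a planned misreading. The mismatch between consented people in the numerator and enrolled people in the denominator is real; its size cannot be judged from the documents. The changes are worth making because they use data already collected.

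**What to change.** - Keep the phase rows as description and drop their p-values. Alternatively, label them as unequal exposure and add events per person-day at risk.
- Add a common-window panel counting events across phases, for example from enrollment to Day 14 and to Day 30 after admission. Footnote that capture starts at consent and that daily observation ends sooner in RP.
- For Overall and the common window, give the risk difference with a 95% CI. Where counts allow, take it from a site- and step-adjusted mixed logistic model. Protocol 16.3.2 already plans mixed logistic models for adverse events, and Fisher's test adjusts for neither site nor step.
- Reword the hypothesis in SAP Table 5 as estimation of the difference in place of equivalence.
- Use enrolled (ITT) participants for both numerator and denominator in the arm columns, and list events in consented but not enrolled people separately.

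The cost is SAP wording and one extra table panel. Event, enrollment and admission dates are already recorded. The remaining drawback is some under-ascertainment after induction, likely greater in RP during Days 7 to 14, which must be stated beside the result.

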10.2 Serious Adverse Events

Serious adverse events (SAEs) are defined in Section 3.2.8. SAEs will be summarized by presenting the number of events, number of participants experiencing SAEs, and the relatedness and type of SAEs by induction procedure.

All SAEs will be coded using MedDRA® dictionary version v25.0. The number and proportion of participants experiencing SAE will be provided by induction procedure and overall. SAEs will be summarized by System Organ Class (SOC) and Preferred Term (PT). The proportion will be calculated as the number of participants who experience the event at least once divided by the number of participants in the induction procedure or overall. Proportions will be calculated at the preferred term level, at the SOC level, and for participants with at least one SAE. If a participant experiences multiple episodes of an event, then the event is only counted once. Detailed listings of SAEs by induction procedure will be provided. The listing will include Participant ID, date of IC, date of enrollment, SAE onset date, description, severity of AE, relatedness to study medication, outcome, resolution date, reason reported as SAE, and MedDRA® coded preferred term and system organ class. Narratives for all serious adverse events will be provided.

10.3 Death

A listing of deaths and narratives by induction procedure will be provided.

10.4 Injection Site Abnormalities

The Injection Site Abnormality (INA) form records any time an injection is given and there is an abnormal reaction observed at the injection site. Injection site abnormalities will be summarized by number of injection site abnormalities, type of abnormality, and the severity of the abnormality. A detailed listing of injection site abnormalities for injections by induction procedure will be provided. The listing will include Participant ID, date of IC, date of enrollment, date of injection, injection number, injection location, abnormality start and resolution date, symptom, severity, and SAE classification.

10.5 Overdoses

The Overdose Questionnaire (ODQ) form assesses each participant's self-reported opioid overdose history, as well as information regarding the most recent overdose event. A summary table of non-fatal opioid overdoses will be provided by induction procedure and by study visit (at baseline and at each post induction visit). At the baseline visit, participants are asked about any opioid overdoses prior to enrollment. At the post-induction visits, participants are asked about opioid overdoses since their last visit. The number of participants with at least one opioid overdose and the number participants with the most recent overdose where NARCAN (naloxone) was used to reverse overdose and resulted in being admitted to the hospital will be reported. A detailed listing of non-fatal opioid overdoses by induction procedure will be provided. The listing will include Participant ID, date of IC, date of enrollment, visit, date of assessment, overdose history, NARCAN use, hospital admission, substance used, and the five questions asked on a scale of 0 to 10.

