7.2 Secondary Outcome Measure(s)

7.2.1 Table 3: Secondary Clinical Outcomes, Outcome Measures and Hypotheses

Outcome	Outcome Measure	Hypothesis
Time from admission to first XR-NTX injection	Days to first XR-NTX injection	Participants in the RP will receive their first injection significantly faster than those in the SP. Significance/Rationale: The RP decreases the time to the first injection (which has a potential to decrease costs and staff burden).
Opioid Craving (VAS) over time	Mean for opioid craving measured by VAS daily during days leading to the first XR-NTX injection, and during post-induction Weeks 1-8	Participants in RP and SP will have comparable intensity of craving during 1) the inpatient treatment period, and 2) during the first week after the first XR-NTX injection. Significance/Rationale: Earlier trial showed comparable craving severity in both procedures (Sullivan et al. , 2017).
Opioid withdrawal (SOWS and COWS) over time	Mean for opioid withdrawal measured by SOWS and COWS score, daily (starting with day of admission) during days leading to the first XR-NTX injection and during post-induction Weeks 1-8	Participants in RP and SP will have comparable severity of opioid withdrawal during: 1) the inpatient treatment period, and 2) during the first four weeks after the first XR-NTX injection. Significance/Rationale: Earlier trial showed comparable withdrawal severity in both procedures (Sullivan et al. , 2017).
Receive second and third injections (binary: did or did not receive second and third dose of XR-NTX)	Proportion of participants that receive second and third injection of XR-NTX (at 4 weeks and 8 weeks, from first injection)	Participants in RP and SP will have comparable rates of treatment retention. Significance/Rationale: Because there is no difference in tolerability of the first and second XR-NTX injections in both study arms, we do not expect differential treatment dropout.
Targeted safety events, overdoses and SAEs, related to study medications	Frequency of targeted safety events, overdose episodes and SAEs by relationship to study medication during the induction period and during eight weeks of post-induction	RP and SP will produce equivalent rates of targeted safety events and SAEs during the induction and during the first eight weeks of treatment with XR-NTX. Significance/Rationale: Careful documentation of SAEs, targeted safety events, and overdose

Outcome	Outcome Measure	Hypothesis

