SOWS	Subjective Opiate Withdrawal Scale
SP	Standard Procedure
SW	Stepped-Wedge
TAU	Treatment as Usual
TLFB	Timeline Followback
TSE	Targeted Safety Event
UDS	Urine Drug Screen
VAS	Visual Analog Scale
XR-NTX	Extended-Release Naltrexone (Vivitrol®)

LIST OF eCRFs

AAS	Adult ADHD Self-Report Screening Scale for DSM-5
AD1	Adverse Event
AD2	Serious Adverse Event Summary
AD3	Serious Adverse Event Medical
ASU	Alcohol and Substance Use
C97	Critical Action Checklist
CMX	Concomitant Medications
COW	Clinical Opioid Withdrawal Scale
CUT	Clinic Urine Toxicology
CVD	COVID-19 Impact Assessment
D97	Study Demographics (RA/RC Administered)
DEM	Demographics
DMA	Daily Medication Administration Log
DSM	DSM-5 Checklist
DTH	Death Form
EIP	End of Induction Survey
ENRA	Enrollment into Segment A
ENRB	Enrollment into Segment B
ENRC	Enrollment into Segment C
ENRD	Enrollment into Segment D
ENRE	Enrollment into Segment E
EO2	End of Medication (Self-Reported)
EOI	End of Induction
EOM	End of Medication
FAM	Family Origin
FC1	Pre-Implementation Fidelity to Implementation Checklist
FC2	Post-Implementation Fidelity to Implementation Checklist
FND	Fagerström Test for Nicotine Dependence
FOO	Fatal Opioid Overdose
GA7	Generalized Anxiety Disorder
GEN	Genetics
HEP	Self-Report of Hepatitis Testing and Treatment
HIV	Self-Report of HIV Testing
INA	Injection Site Abnormality
INB	Induction Buprenorphine
INN	XR-NTX Administration
LDN	Low Dose Naltrexone Titration
LIF	Locator Information Form

M97	Timeline Followback Medications
MGT	Medical Management
MHA	Mental Health Follow-up Assessment
MHX	Medical Psychiatric History
MJA	Cannabis Use Assessment
MTV	Motivation Scale
NM2	Non-Medical and Other Services - Page 2
NMS	Non-Medical and Other Services
OCI	Opioid Craving Scale
OCO	Opioid Craving Scale
ODQ	Overdose Questionnaire
OES	Opioid Effect Scale
OLC	Organization Level Clinical Implementation
OR1	Pre-Implementation Organizational Readiness to Change Assessment
OR2	Post-Implementation Organizational Readiness to Change Assessment
PBC	Pregnancy and Birth Control Assessment
PCL	PTSD Checklist for DSM-5
PDA	Panic Disorder Assessment
PHQ	Patient Health Questionnaire (PHQ-9)
PO1	Pregnancy Outcome 1
PO2	Pregnancy Outcome 2
PO3	Pregnancy Outcome 3
PO4	Pregnancy Outcome 4
PRG	Confirmed Pregnancy and Outcome
PRO	PROMIS
PSA	Prisoner Status Assessment
PST	Psychosocial Treatment
QLP	Quality of Life
S97	Additional Demographics
SBW	The Subjective Opiate Withdrawal Scale
STC	Study Completion
T97	Timeline Followback

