2.1.2 Secondary Objectives

The key secondary objective is to summarize the below outcome to confirm expected characteristics of the RP compared to SP:

1. Time to receipt of first injection of XR-NTX from day of admission for participants that receive first injection of XR-NTX while on the unit.

Additional key secondary objectives are to compare the below outcomes of RP versus SP for all enrolled participants, intent-to-treat (ITT) population.

2. Craving for opioids measured by Visual Analog Scales (VAS).
3. Opioid withdrawal symptoms as measured by the Subjective Opioid Withdrawal Scale (SOWS) and the Clinical Opiate Withdrawal Scale (COWS).
4. Safety, as measured by overdose questionnaire, targeted safety events and serious adverse events.

Other secondary objectives are to compare the below outcomes of RP vs. SP for participants who receive the first injection while on the unit.

5. Retention in the trial to receive the second and the third XR-NTX injections.
6. Craving for opioids measured by Visual Analog Scales.
7. Opioid withdrawal symptoms following XR-NTX injection as measured by the Subjective Opioid Withdrawal Scale.
8. Safety, as measured by overdose questionnaire, targeted safety events and serious adverse events.
9. Opioid abstinence, as measured by the Timeline Followback (TLFB) (self-report days using opioids) and proportion of opioid-positive urine tests (UDS).

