8.4 Definition of the Secondary Outcome Measures

Key secondary analyses to be conducted by the DSC:

A key secondary objective is to summarize the below outcome to confirm expected characteristics of the RP compared to SP:

1. The time to receipt of first injection of XR-NTX as measured by the number of days from admission to first XR-NTX injection. This will be conducted on the successfully inducted population only. Day of admission is defined as Day 1 (E97ADMDT) as recorded on the ENRC or ENRD forms, and day of first XR-NTX injection (EOIINJDT) is captured on the End of Induction form (EOI). It will be calculated as Date of injection (EOI.EOIINJDT) – Date of admission (ENRC/ENRD.E97ADMDT) +1.

Additional key secondary objectives are to compare the below outcomes of RP versus SP for all enrolled participants (ITT population).

2. Craving for opioids measured by Visual Analog Scales (VAS) as captured daily on the self-reported inpatient opioid craving form (OCI) during induction phase. The OCI form collects intensity of craving both at time of assessment and within the last 24 hours prior to assessment. If either measurement is collected multiple times on the same assessment date, the average measurement will be used for analysis.
3. Opioid withdrawal symptoms as measured by the Subjective Opioid Withdrawal Scale (SOWS) and the Clinical Opiate Withdrawal Scale (COWS). SOWS is captured on the SBW form at baseline and daily during induction phase. COWS is captured on the COW

form starting with day of admission and daily during the induction phase leading to the first XR-NTX injection. Note that during induction, COWS may be measured multiple times per day while SOWS is expected to be assessed only once per day. If multiple SOWS measures are collected on the same assessment date, the average measurement will be used for analysis. If multiple COWS measures are collected on the same assessment, the peak measurement will be used.

4. Retention in the trial to receive at least one XR-NTX injection after the first injection as captured on the XR-NTX Administration (INN) form.
5. Safety, as measured by targeted safety events, overdoses, and serious adverse events related to study medication during the induction phase and during eight weeks of post-induction. Detail on safety outcome analysis is provided in Section 9.0.

Other secondary analyses to be conducted by LN:

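### The overdose outputs count only self-reported non-fatal overdoses, so no planned output shows how many participants in each arm had any opioid overdose

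*SAP*

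**What the plan says.** The outcome is defined broadly. Protocol Table 3 gives the measure as "Frequency of targeted safety events, overdose episodes and SAEs by relationship to study medication during the induction period" and the eight weeks of post-induction treatment. SAP 8.4, key secondary item 5, has "Safety, as measured by targeted safety events, overdoses, and serious adverse events related to study medication" over the same periods. Neither restricts overdoses to non-fatal ones. The objective in SAP 2.1.2 (and Protocol 5.2) is worded by instrument: "Safety, as measured by overdose questionnaire, targeted safety events and serious adverse events".

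The output is narrower. SAP 10.5 opens with its source: "The Overdose Questionnaire (ODQ) form assesses each participant's self-reported opioid overdose history". It then plans that "A summary table of non-fatal opioid overdoses will be provided by induction procedure and by study visit". The shells for Table 54 and Listing 5, and their entries in SAP 18.0, carry the same non-fatal label.

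Fatal events go elsewhere. SAP 10.3 says "A listing of deaths and narratives by induction procedure will be provided". Death is an SAE criterion (SAP 3.2.7), and Protocol 12.3.4 has on-study overdoses that meet SAE criteria reported as SAEs too. Table 51 counts participants by MedDRA term and procedure, with overdose among its example terms. The SAP's list of eCRFs includes a form named "Fatal Opioid Overdose" (FOO), but no analysis section or shell names it.

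**The concern.** The plan promises a safety component called overdoses, and the table bearing that name excludes the most severe form of the event. The questionnaire needs a living respondent who attends, so it cannot record a death.

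This matters in this trial. Protocol 4.1.2 describes dropout as raising the risk of relapse that leads to overdose, disability and death, and Appendix B puts overdose first among the study-specific risks. Participants who fail induction are the ones who leave without the injection. They are seen only at Weeks 4 and 8 (Protocol 10.5.5), and their number by procedure is the primary outcome. Someone asking how many participants in each arm had an opioid overdose after enrolment would turn to Table 54 and get an incomplete count, without a planned output that completes it.

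**Working it through.** **1. What each output can supply.**

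- Table 54 and Listing 5 cover non-fatal overdoses from the questionnaire. They miss participants whose only on-study overdose was fatal.
- The deaths listing covers every death, with cause and narrative, by procedure. It is a listing, so it gives no count or percentage per arm.
- Table 51 counts participants with each serious event by preferred term. An overdose row there would mix fatal with serious non-fatal events, is not specific to opioids, and leaves out questionnaire-reported overdoses that did not meet SAE criteria.
- A non-fatal overdose that met SAE criteria appears in both Table 54 and Table 51. Adding the two therefore counts that participant twice, and using either alone undercounts. The total can be recovered only by matching participants across forms, which no section plans.

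**2. The denominator of Table 54.** No footnote defines it for the row counting participants with at least one overdose. SAP 18.0 assigns the table to the safety population, which is everyone who signed consent (SAP 3.1.4). The neighbouring Table 55 shell carries figures that show the convention: 20/190 = 10.5% (SP), 38/225 = 16.9% (RP) and 58/415 = 14.0% (total) in the post-induction row. These match the printed percentages, so that table divides by the full arm, not by attendees or survivors. By analogy a participant who died would stay in the Table 54 denominator. This is an inference.

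**3. Effect of one omitted death.** In an arm of 225, 1/225 = 0.44 points; in an arm of 190, 1/190 = 0.53 points.

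**4. Range under assumed counts.** The documents give no overdose rates, so every count here is an assumption. Arm sizes are those in the Table 55 shell (190 SP, 225 RP), and those who die are assumed not to have reported an earlier non-fatal overdose. The non-fatal count is set equal in both arms. Differences are RP minus SP in percentage points.

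| Non-fatal per arm | Table 54 SP / RP | Difference shown | Adding 1 RP death | 3 RP deaths | 5 RP deaths | 3 SP deaths |
|---|---|---|---|---|---|---|
| 2 | 1.1% / 0.9% | -0.2 | +0.3 | +1.2 | +2.1 | -1.7 |
| 5 | 2.6% / 2.2% | -0.4 | 0.0 | +0.9 | +1.8 | -2.0 |
| 10 | 5.3% / 4.4% | -0.8 | -0.4 | +0.5 | +1.4 | -2.4 |

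For example, 5 non-fatal and 3 fatal in RP give 8/225 = 3.6% against 5/190 = 2.6%, a difference of +0.9 points before rounding the two rates. The sign can change in either direction of imbalance. No scenario run gives a Fisher p-value below 0.05; the smallest is 0.19 (2/190 against 7/225).

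**The case against.** The strongest reply is that the key secondary outcome already contains fatal overdoses. SAP 2.1.2 and Protocol 5.2 name three components: the overdose questionnaire, targeted safety events and SAEs. The questionnaire is thus a declared instrument, and a fatal overdose enters the same outcome as an SAE. The table is openly labelled non-fatal, so it makes no claim about deaths. Listings carry participant identifiers, so an analyst could resolve the overlap. SAP 8.5 plans only frequencies for overdoses, Fisher's exact test is specified only for targeted safety events (SAP 10.1), and SAP 11.0 calls the key secondaries non-confirmatory.

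Most of this stands, and it limits the point. A reader might infer that someone who dies of overdose is treated as overdose-free in the trial's safety comparison. The documents do not support that: the omission is confined to Table 54 and Listing 5, and even there a participant who had already reported a non-fatal overdose in the same period is still counted. A reader might also infer that the fatal-overdose form goes unused. The SAP is only silent: section 10.3 names no source form at all, so the form may well feed the deaths listing. Nor is there any basis for saying which procedure would be favoured.

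The reply does not reconcile the questionnaire wording of the objectives with the unrestricted wording of SAP 8.4 and Protocol Table 3. It also does not supply the missing count. That participants could be matched across listings shows the count is feasible, not that it is planned.

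**Conclusion.** The dedicated overdose outputs do not deliver the overdose component as SAP 8.4 and Protocol Table 3 define it, and no planned output gives participants with any opioid overdose by induction procedure. This is a gap in a descriptive safety summary. It does not affect the primary analysis or any planned test, and fatal overdoses remain visible by procedure elsewhere.

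The size is unknown. What can be said is that each omitted death lowers the figure for an arm of 225 by 0.44 points, if the denominator is the full arm. With few events that is enough to change the sign of a small difference, though none of the assumed scenarios amounts to statistical evidence of one. The change is worth making because it is cheap and the omitted event is the most severe one.

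**What to change.** In SAP 10.5 and Table 54, add a row by induction procedure for participants with at least one opioid overdose after enrolment. Take fatal events from the FOO form, the Death form and SAE records, and non-fatal events from the questionnaire and SAE records. Count each participant once, show fatal and non-fatal as sub-rows, and state the denominator in a footnote. Retitle the table so that it is no longer confined to non-fatal events, and name this row as the overdose component of key secondary item 5.

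The new row should be all-cause. Keep beside it the breakdown by relationship to study medication that Table 3 specifies, so that the outcome is completed and not replaced.

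The cost is SAP wording, one derived variable from forms already collected, and modest reconciliation across forms to avoid double counting. No visit, form or clinical procedure changes.
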